5.3 Randomization and Blinding

After eligibility is determined, subjects will be randomized to 1 of the treatment groups as described in Sections 3.1 and 5.1. Subjects will be randomized using the centralized randomization system, according to a computer-generated randomization list, and stratified by disease severity. Sentinel subject randomization will not be stratified by disease severity. Treatment group assignment will be blinded to subjects, clinicians, Sponsor study team, CRO study team, and Investigators. Specific individuals from the bioanalytical CRO and Sponsor's PK group will have access to the randomization code to allow for ongoing analysis of bioanalytical samples from the subjects treated with razuprotafib and to provide PK analysis results for the DRC reviews.

5.4 Breaking the Blind

Unblinding by request of an Investigator should occur only in the event of an emergency or AE for which it is necessary to know the study drug to determine an appropriate course of therapy for the subject. If the Investigator must identify the treatment assignment of an individual subject, the Investigator or qualified designee should request the treatment assignment from the centralized randomization system. They should not attempt to get this information from the site's unblinded pharmacist or qualified designee. The Investigator is advised not to reveal the study drug assignment to other site or Sponsor personnel.

Prior to unblinding, and if the situation allows, the Investigator should consult with the Sponsor's Medical Monitor. If this is impractical, the Investigator must notify the Sponsor's Medical Monitor as soon as possible, without revealing the treatment assignment of the unblinded subject. The Investigator must document the subject identification and the date and time for breaking the blind and must clearly explain the reasons for breaking the blind.

Medically necessary care should not be delayed for unblinding information (ie, the Investigator should treat the subject based on the subject's signs/symptoms without waiting for the unblinding process to be completed).

Subjects who are unblinded and discontinue study drug should continue to complete all safety assessments at subsequent study visits up to and including Day 28, unless the subject or LAR withdraws consent or is lost to follow-up.

5.5 Drug Supplies

5.5.1 Formulation and Packaging

The drug product formulation contains AKB-9778-sodium salt ready to dose, preservative free, isotonic, sterile solution (20 mg/mL or 40 mg/mL) in a 3 mL borosilicate vial fitted with a 13 mm septum and aluminum flip top seal. A dose volume of 0.50 mL of 20 mg/mL solution will deliver a dose of 10 mg, a dose volume of 0.75 mL of 20 mg/mL solution will deliver a dose of 15 mg, a dose volume of 0.50 mL of 40 mg/mL solution will deliver a dose of 20 mg, and a dose volume of 0.75 mL of 40 mg/mL solution will deliver a dose of 30 mg. The formulation also contains 15% hydroxypropyl-beta-cyclodextrin (Betadex), United States Pharmacopeia (USP), used as a solubilizer, and 1.2% mannitol, USP, for tonicity modification. The formulation is controlled to pH 4.0 to 8.6.

Placebo for razuprotafib (sterile normal saline) will be sourced locally by the site as a parenteral formulation ready to dose. The volume of placebo will match the volume of razuprotafib based on the dose(s) of razuprotafib in each treatment group in Part 1 (Step 1 and Step 2) and in Part 2. Refer to the Pharmacy Manual for specific requirements of sterile normal saline.

Razuprotafib will be provided in an open-label format that is compliant with International Council for Harmonisation (ICH) Good Clinical Practice (GCP) guidelines. The placebo will be sourced locally and provided with the commercially available product label.

5.5.2 Study Drug Preparation and Dispensing

Study drug will be prepared locally by an unblinded pharmacist. Syringes will be prepared using aseptic technique prior to administration and stored for no more than 24 hours. One vial of razuprotafib (20 mg/mL or 40 mg/mL) contains sufficient quantity to prepare 3 doses for TID administration per subject per day. Prepared syringes will be labeled as required per local standard operating procedures (SOPs) to ensure proper identification and to protect the study blinding. Refer to the Pharmacy Manual for specific study drug preparation instructions and specifications for the disposable sterile syringe.

5.5.3 Study Drug Administration

A volume of 0.50 mL or 0.75 mL of study drug will be administered TID (Q8H) by SC injection to the abdomen. Subjects will be dosed for 7 days or until discharge from the hospital (or death), whichever occurs first. Subjects will be in the supine position during dosing, and they must remain supine with their head no higher than 45° until the vital sign assessment is completed 90 minutes following dosing. The first study drug administration must occur within 12 hours after randomization. Study drug should be administered at the same nominal times (± 1 hour) for each Q8H dose throughout the Treatment Period. Prior to the initiation of Part 2, the DRC may make a recommendation to increase the study drug dosing duration to up to 14 days. Refer to the Pharmacy Manual for specific study drug administration instructions.

5.5.4 Treatment Compliance

To ensure treatment compliance, all doses will be administered by the site staff.

The exact time of study drug administration and the volume of study drug administered will be recorded in the eCRF.

5.5.5 Storage and Accountability

At the investigational site, study drug will be stored in a secure area with access limited to authorized personnel. Active drug product vials will be stored and maintained at USP controlled room temperature, 15°C to 25°C (59°F to 77°F), with transient excursions of up to 30°C permitted.

Prepared syringes can be stored for no more than 24 hours at USP controlled room temperature, 15°C to 25°C (59°F to 77°F), with excursions of up to 30°C permitted.

The responsible pharmacist at the investigational site must keep an ongoing and accurate inventory of study drug shipments received and the number of unused and used vials per subject. A full reconciliation of study drug inventory will be performed at the end of the study, and the results of the inventory will be recorded in the Drug Accountability Form.

Used vials will be retained for the duration of the study or until verified by the Clinical Research Associate (CRA) as outlined below. All administered syringes and/or prepared syringes that are beyond the defined 24-hour holding period will be discarded locally in a sharps container as per local SOPs and/or as biohazardous exposure control plans require.

At the conclusion of the study, the CRA will account for all used and unused study drug. After completion of the study, or if it is prematurely terminated, all unused materials will be returned to the Sponsor or a delegate or destroyed locally at the site following an approved SOP and/or vendor. Additional information can be found in the Pharmacy Manual.

5.6 Prior and Concomitant Medications and/or Procedures

5.6.1 Excluded Medications and/or Procedures

During the period of hospitalization **prior to randomization**, the following medications and/or procedures are prohibited:

- Invasive mechanical ventilation; or oxygen delivered by ECMO;
- Pressor support; and
- Sensitive CYP2C8 substrates (eg, repaglinide, paclitaxel, or cerivastatin) and CYP2C8 inhibitors (eg, gemfibrozil, fluvoxamine, or ketoconazole).

After randomization, the following medications and/or procedures are prohibited:

- Sensitive CYP2C8 substrates (eg, repaglinide, paclitaxel, or cerivastatin) and CYP2C8 inhibitors (eg, gemfibrozil, fluvoxamine, or ketoconazole).

Note: CYP2C8 substrates or inhibitors should be withheld if possible. However, any medications that are CYP2C8 substrates or inhibitors that are required for standard of care can be provided if deemed necessary for management of the patient by the Investigator. Subjects that receive these medications, as standard of care for COVID-19, should not be withdrawn.

5.6.2 Allowed Medications and/or Procedures

Use of medications for COVID-19, such as remdesivir, antivirals, and dexamethasone, are permitted for the management of COVID-19.

5.6.3 Documentation of Prior and Concomitant Medication Use and/or Procedures

Any therapies that are being used for other non-COVID-19 indications but may have an impact on SARS-CoV-2 and COVID-19 (eg, IL-6 inhibitors or hydroxychloroquine for rheumatological conditions) should be listed as concomitant medication along with the time, dose, and duration of their administration.

Any treatment given in addition to the study drug during the study is regarded as a concomitant medication and must be recorded on the appropriate eCRF.

Any relevant medications received in the 14 days prior to study drug administration must be recorded on the appropriate eCRF, along with the reason for use, dates of administration, and dosages.

Concomitant medications should be kept to a minimum during the study. However, if these are considered necessary for the subject's welfare, are unlikely to interfere with the study drug, and not specifically excluded, then they may be given at the discretion of the Investigator and recorded in the subject's source documents and the eCRF. Investigators are encouraged to discuss specific medications with the Medical Monitor or Sponsor when in question.

Any care decisions that are made due to resource limitation (eg, ventilation not available) must be documented.

Data surrounding major changes in background therapy will be collected. The standard of care that is followed for each subject and site must be recorded. If standard of care therapies are not able to be delivered due to resource limitations, this should also be recorded.

Any reasons for discontinuation of ventilation must be recorded on the appropriate eCRF, including all data related to clinical decision making that guides removal from mechanical ventilation in relation to clinical deterioration or lack of clinical response.

6 STUDY PROCEDURES

Study procedures will follow the Schedule of Procedures ([Appendix A](#)).

7 EFFICACY, PHARMACODYNAMIC, AND PHARMACOKINETIC ASSESSMENTS

The efficacy endpoints include the following:

- Proportion of subjects alive and free of respiratory failure at Day 28;
- Proportion of subjects alive and free of respiratory failure at Day 7;
- Change in PaO₂:FiO₂ ratio from baseline to Day 7 (or discharge) and baseline to Day 28 (or discharge);
- Length hospitalized and free of respiratory failure from baseline to Day 7 and baseline to Day 28 or death;
- Length of hospitalization from baseline to Day 7 and baseline to Day 28 or death;
- Proportion of subjects who improve by ≥ 2 categories on the NIAID 8-point ordinal scale from baseline to Day 7 and baseline to Day 28;
- Proportion of subjects who worsen by ≥ 2 categories on the NIAID 8-point ordinal scale from baseline to Day 7 and baseline to Day 28;
- All-cause mortality at Day 7 and Day 28;
- Length of ICU stay from baseline to Day 28 or death;
- Number of subjects in each category of the NIAID 8-point ordinal scale at Day 7 and Day 28;
- Time to return to prehospitalization oxygen requirement; and
- Proportion of subjects who were discharged and remained free of respiratory failure prior to Day 7 and Day 28.

The pharmacodynamic and PK endpoints include the following:

- Change from baseline in CRP and D-dimer;
- Change from baseline in systemic biomarkers of vascular leakage and inflammation (ie, Angpt-2, IL-6, IL-8, TNF α , and HMGB-1);
- Summary of plasma concentrations of biomarkers at each sampling time point for each treatment group; and
- Summary of plasma razuprotafib concentrations for the samples collected on Day 1 and Day 6.

7.1 Hospitalization and Ventilator Data

The length of hospitalization will include all days that the subject is admitted to the hospital. For subjects who are discharged and readmitted to the hospital, the length of hospitalization will include the days after readmission.

Hospitalization days will be counted in 24-hour periods; any partial days will be counted as a whole day.

Days that subjects are weaning off and on the ventilator will be counted as days of respiratory failure.

7.2 National Institute of Allergy and Infectious Diseases 8-Point Ordinal Scale

The NIAID 8-point ordinal scale includes the following grades:

1. Death;
2. Hospitalized, on invasive mechanical ventilation or ECMO;
3. Hospitalized, on noninvasive ventilation or high-flow oxygen devices;
4. Hospitalized, requiring supplemental oxygen;
5. Hospitalized, not requiring supplementation oxygen – requiring ongoing medical care (COVID-19 related or otherwise);
6. Hospitalized, not requiring supplemental oxygen – no longer requires ongoing medical care;
7. Not hospitalized, limitation on activities and/or requiring home oxygen; and
8. Not hospitalized, no limitations on activities.

7.3 Biomarker Analysis

Blood sampling for biomarkers associated with coagulation, inflammation, and vascular leakage (CRP, D-dimer, Angpt-2, IL-6, IL-8, TNF α , and HMGB-1) will occur at Screening and on Day 7 (or at discharge if subject is discharged prior to Day 7) for all subjects. If the study drug dosing duration is increased to up to 14 days, blood sampling for biomarkers will also occur on the last day of dosing. For all subjects remaining hospitalized on Day 14 or beyond, blood sampling for biomarkers will also occur on Day 28 or the day of hospital discharge, whichever occurs first. CRP and D-dimer biomarker analysis will be performed at the local laboratory. Vascular leakage and inflammation biomarker (Angpt-2, IL-6, IL-8, TNF α , and HMGB-1) analysis will be performed at a central laboratory.

Blood samples for vascular leakage and inflammation biomarker analysis will be stored at a central laboratory for reanalysis if needed and will be destroyed no later than 6 months after the final clinical study report has been submitted to the relevant regulatory authority(ies).

All blood samples for biomarker analysis will be de-identified at the time of sample collection.

7.4 Pharmacokinetic Analysis

Blood samples for PK analysis will be collected on Day 1 and Day 6 at 30 (± 15) minutes and 90 (± 15) minutes after the first study drug dose of the day. The exact time of study drug administration and the exact time of blood sample for PK analysis collection will be recorded on the eCRF. PK analysis will be performed at a central laboratory. Blood samples for PK analysis will be collected for all subjects; however, samples for subjects randomized to placebo will not be analyzed. Blood samples for PK analysis will be collected for all subjects in Part 1; blood samples for PK analysis may be collected for subjects in Part 2, after review of the PK data in Part 1.

8 SAFETY ASSESSMENTS

8.1 Adverse Events

An AE is defined as any untoward medical occurrence in a clinical investigation subject administered a pharmaceutical product, which does not necessarily have a causal relationship with this treatment. An AE can therefore be any unfavorable and/or unintended sign (including an abnormal laboratory finding), symptom, or disease temporally associated with the use of an investigational medicinal product, whether or not related to the investigational medicinal product. All AEs, including observed or volunteered problems, complaints, or symptoms, are to be recorded on the appropriate eCRF.

AEs, which include clinical laboratory test variables, will be monitored and documented from the time of the first dose of study drug until Day 28. Subjects should be instructed to report any AE that they experience to the Investigator, whether or not they think the event is due to study treatment. Beginning at the date of the first dose of study drug, Investigators should make an assessment for AEs at each visit and record the event on the appropriate AE eCRF.

Wherever possible, a specific disease or syndrome rather than individual associated signs and symptoms should be identified by the Investigator and recorded on the eCRF. However, if an observed or reported sign or symptom is not considered a component of a specific disease or syndrome by the Investigator, it should be recorded as a separate AE on the eCRF. Additionally, the condition that led to a medical or surgical procedure (eg, surgery, endoscopy, tooth extraction, or transfusion) should be recorded as an AE, not the procedure itself.

Any medical condition already present at the date of the first dose of study drug should be recorded as medical history and not be reported as an AE unless the medical condition or signs or symptoms present at baseline changes in severity, frequency, or seriousness at any time during the study. In this case, it should be reported as an AE.

Clinically significant abnormal laboratory or other examination findings that are detected during the study or are present at the date of the first dose of study drug and significantly worsen during the study should be reported as AEs, as described below. The Investigator will exercise his or her medical and scientific judgment in deciding whether an abnormal laboratory finding or other abnormal assessment is clinically significant. Clinically significant abnormal laboratory values occurring during the clinical study will be followed until repeat tests return to normal, stabilize, or are no longer clinically significant. Abnormal test results that are determined to be an error should not be reported as an AE. Laboratory abnormalities or other abnormal clinical findings should be reported as an AE if any of the following are applicable:

- If an intervention is required as a result of the abnormality;
- If action taken with the study drug is required as a result of the abnormality; or
- Based on the clinical judgment of the Investigator.

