8.2 Serious Adverse Events/Drug Reaction

An AE or adverse reaction is considered serious if, in the view of either the Investigator or Sponsor, it results in any of the following outcomes:

- Death;

- Is life-threatening;

Note: The term “life-threatening” in the definition of “serious” refers to an event in which the subject was at immediate risk of death at the time of the event. It does not refer to an event that hypothetically might have caused death if it were more severe.

- Requires hospitalization or prolongation of existing hospitalizations;

Note: Any hospital admission with at least 1 overnight stay will be considered an inpatient hospitalization. An emergency room or urgent care visit without hospital admission will not be recorded as an SAE under this criterion, nor will hospitalization for a procedure scheduled or planned before signing of informed consent, or elective treatment of a pre-existing condition that did not worsen from baseline. However, unexpected complications and/or prolongation of hospitalization that occur during elective surgery should be recorded as AEs and assessed for

seriousness. Admission to the hospital for social or situational reasons (ie, no place to stay, live too far away to come for hospital visits, respite care) will not be considered inpatient hospitalizations.

- Results in persistent or significant disability/incapacity or substantial disruption of the ability to conduct normal life functions;
- Is a congenital anomaly/birth defect; or
- Is an important medical event.

Note: Important medical events that do not meet any of the above criteria may be considered an SAE when, based upon appropriate medical judgment, they may jeopardize the subject and may require medical or surgical intervention to prevent 1 of the outcomes listed above. Examples of such medical events include allergic bronchospasm requiring intensive treatment in an emergency room or at home, blood dyscrasias or convulsions that do not result in inpatient hospitalizations, or the development of drug dependency.

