8.7 Safety Assessments

The safety endpoints include the following:

- Number of subjects with any SAE; and
- Number of subjects with any treatment-emergent AE.

Safety will be determined by evaluating clinical laboratory findings (blood chemistry, hematology, and coagulation), vital signs (blood pressure, heart rate, SpO₂ [for non-ventilated subjects only], and respiratory rate), 12-lead electrocardiograms, and AEs reported during the study.

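### The two headline safety endpoints count all causes with no row set apart for COVID-19 progression, so a benefit on COVID-19 can dilute or, at some rates, offset a drug-caused excess

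*Protocol*

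**What the plan says.** **Safety side.** Protocol 8.7 names two safety endpoints: "Number of subjects with any SAE" and "Number of subjects with any treatment-emergent AE". SAP 2.3.3 repeats them. Protocol 8.1 is all-cause: "An AE is defined as any untoward medical occurrence in a clinical investigation subject administered a pharmaceutical product". A condition present at first dose goes to medical history "unless the medical condition or signs or symptoms present at baseline changes in severity, frequency, or seriousness at any time during the study". For laboratory and other findings, the same section counts those that "are present at the date of the first dose of study drug and significantly worsen during the study should be reported as AEs". The SAE criteria in Protocol 8.2 include death, life-threatening events and "Requires hospitalization or prolongation of existing hospitalizations", with no exemption for the disease under study. SAP 3.6.1 defines a TEAE by timing alone. The few carve-outs in Protocol 4.4.2, such as fever present at entry, apply only to the study-termination criteria.

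**Efficacy side.** Protocol 7 includes "Proportion of subjects alive and free of respiratory failure at Day 28", all-cause mortality at Days 7 and 28, and length of hospitalization. SAP 2.3.1 keeps these.

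**Planned tables.** SAP 3.6.1 gives subject and event counts for TEAEs overall and by maximum severity, and for drug-related, serious, discontinuation and fatal events, each by system organ class and preferred term. SAP 3.6.2 to 3.6.4 add laboratory, vital-sign and ECG summaries. No row gives subjects with an SAE or TEAE other than COVID-19 progression.

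**The concern.** A subject whose COVID-19 worsens to respiratory failure or death is counted under efficacy and again under any SAE. If razuprotafib works, its arm loses some of these events, and that loss is netted against any SAEs the drug causes. If it does not work, a common background of disease events still shrinks the visible excess. Safety is a primary objective (Protocol 2.1) and the main focus of Part 1 (Protocol 3.1), so the headline counts matter.

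The relatedness row is a weak safeguard. Protocol 8.1.3 reserves *Yes* for events where no other cause can be identified, and in hospitalized COVID-19 patients another candidate cause is nearly always at hand. Preferred-term rows cannot be added up to a subject total, because one subject may have several events. A split devised later would be labelled post hoc under SAP 3.4, and would be open to the suspicion that the terms were chosen with the arms known.

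**Working it through.** **The plan's own figure.** There is none to reproduce. Protocol 9.2.5 and SAP 2.2.4 say that no formal sample-size assessment was made, and neither document gives an AE or SAE rate. Every rate below is an assumption.

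**Inputs (assumed).** COVID-19 progression SAEs: c = 25% on placebo; 25%, 20% or 15% on razuprotafib. Other background SAEs: o = 5% in both arms. Drug-caused SAEs: h = 10% on razuprotafib, 0 on placebo. The three sources are taken as independent.

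**Formula.** P(any SAE) = 1 − (1 − c)(1 − o)(1 − h).

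Placebo: 1 − 0.75 × 0.95 = 28.75%.

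| Benefit on COVID-19 SAEs | Any SAE, razuprotafib | Difference from placebo |
|---|---|---|
| None (c = 25%) | 1 − 0.75 × 0.95 × 0.90 = 35.9% | +7.1 points |
| 5 points (c = 20%) | 1 − 0.80 × 0.95 × 0.90 = 31.6% | +2.85, about +2.9 points |
| 10 points (c = 15%) | 1 − 0.85 × 0.95 × 0.90 = 27.3% | −1.4 points |

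**Progression events excluded.** Placebo 5.0%; razuprotafib 1 − 0.95 × 0.90 = 14.5%; difference +9.5 points in all three cases.

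**What drives the result.** Mainly the size of the benefit, not the placebo rate. With a 10-point benefit, 20% v 10% gives 24.0% v 23.05% (−0.95), and 30% v 20% gives 33.5% v 31.6% (−1.9).

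**Exact offset.** Setting the arms equal gives (1 − c₀) = (1 − c₁)(1 − h); o drops out. So h* = 1 − (1 − c₀)/(1 − c₁).
- c₀ = 25%, c₁ = 20%: h* = 1 − 0.75/0.80 = 6.25%.
- c₀ = 25%, c₁ = 15%: h* = 1 − 0.75/0.85 = 11.8%.
- For h = 10% and c₀ = 25%, the offset is exact at c₁ = 1 − 0.75/0.90 = 16.7%, a benefit of 8.3 points.
- Over placebo rates of 15% to 35% and risk ratios of 0.8 or 0.6, h* runs from 3.4% to 17.7%.

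A harm above h* still shows as an excess, though a reduced one.

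**Any TEAE.** Let t be the share of placebo subjects with a TEAE from the disease course, and let 10% have a drug-caused TEAE. With no benefit the difference is (1 − t) × 0.10: +3, +2 and +1 points at t = 70%, 80% and 90%. If the drug also cuts disease TEAEs by a relative 10%, the difference is 1 − (1 − 0.9t)(0.90) − t: −3.3, −5.2 and −7.1 points.

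**The case against.** All-cause counts are a legitimate choice and contradict nothing in the documents. No test of the safety endpoints is planned, so no formal decision turns on them. System organ class rows are themselves subject-level totals, and severity, discontinuation and death are tabulated. Vital signs are summarized as change from pre-dose for each dose (SAP 3.6.3), which captures directly the known drug effect, a transient fall in blood pressure (Protocol 1.2 and 5.2). The arithmetic rests on assumed rates, and with little or no benefit the harm is diluted rather than hidden. All of this stands, and it confines the point to the headline counts. It does not supply the missing row.

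Two stronger readings are tempting, and the documents support neither.

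- A reader might infer from *changes* in Protocol 8.1 that recovery is an AE too, which would push any TEAE toward every subject in each arm. The definition opening that section requires an untoward occurrence, the rule for findings requires significant worsening, and Protocol 8.1.3 requires a severity grade for every AE. Read as a whole, the section does not make improvement an AE.
- A reader might infer that the safety endpoints simply re-measure efficacy. They overlap but differ. Efficacy status is taken on Day 7 or Day 28, while an SAE counts at any time from first dose to Day 28. A subject who deteriorates on Day 4 and recovers can be an SAE and an efficacy success. One enrolled on high-flow oxygen within the respiratory-failure definition, and still on it at Day 28 without worsening, is an efficacy failure but need not be an SAE. The safety counts also include all non-COVID events.

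**Conclusion.** The point holds in a limited form. Any SAE and any TEAE mix disease course with drug harm, and no planned subject-level row separates them. Under the assumed rates, a true excess of 9.5 points in SAEs other than progression appears as +7.1, about +2.9 or −1.4 points in the any-SAE count, as the benefit goes from none to 5 to 10 points. Dilution needs only a sizeable background of disease events; full offset needs a benefit large enough relative to the harm. These figures rest on assumed rates and on independence. If drug-caused SAEs fall mostly in subjects who already have a COVID-19 SAE, the visible difference is smaller still.

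The rest of the safety evaluation is not undermined. This is a cheap improvement to a primary objective, not a flaw that invalidates the safety analysis. The wording in Protocol 8.1 is a clarification only.

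**What to change.** **Tables.** In Protocol 9.2.4 and SAP 3.6.1, keep the all-cause SAE and TEAE rows. Beside each add, by arm, the number and percentage of subjects with at least one SAE (or TEAE) outside a MedDRA term list for COVID-19 progression. Fix the list before unblinding, in the MedDRA version used to code AEs. Candidate terms are COVID-19 pneumonia, hypoxia, respiratory failure, and deaths attributed to these. State that harm is read from both rows. AE and SAE reporting duties do not change.

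**Wording.** In Protocol 8.1, replace *changes* with *worsens* in the rule for conditions present at baseline, to match the AE definition and the rule for laboratory and other findings.

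**Cost.** A term list, one extra row beside each all-cause row, and one word in the protocol; no new data. The downside is that a drug-caused respiratory event or death could be filed as COVID-19 and drop out of the new row, which is why the all-cause row stays beside it.
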